10.6.1 Headache Response

Headache pain free at 2 hours will be defined as a reduction in headache severity from moderate (2) or severe (3) at baseline to none (0) two hours after dosing with study drug. MBS free at 2 hours will be defined as a 'no' response to the presence of the symptom (either nausea, phonophobia, or photophobia) that was identified as MBS at predose, 2 hours after dosing with study drug.

A qualifying migraine is defined as a migraine treated with study drug within 4 hours of onset

Subjects taking rescue medication within the first two hours or who fail to record headache severity at 2 hours will be assumed to be non-responders in the mITT and the ITT analyses.

A subject is defined to have used rescue medication within the first two hours post dosing if at least one medication is documented in the rescue medication log in the subject electronic diary for which:

$0 \text{ (min)} < \text{date/ time rescue medication (diary)} - \text{date/ time of dosing (diary)} < 120 \text{ (min)}$.

Subjects who do not provide a headache pain severity rating at baseline or who use other medication prior to the study drug for the study migraine attack will be assumed to be non-responders for the mITT and ITT analysis.

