### **5.4 Analysis of First and Second Doses**

Any analyses based on first dose will only include data observed up to the time of dosing with a second dose. These summaries will be presented based on the first dose taken. The exception to this is the secondary endpoints at the 2-hour time point; if a second dose is taken before the 2-hour time point, the subject will still be included in the summary at 2 hours and will be analysed as having not achieved headache pain-free or MBS-free status at 2 hours.

Any analyses based on the second dose will only include data observed on or after the time of dosing with a second dose. Analyses based on the second dose will be done for both the rescue and recurrence subpopulations.

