### **11.1 Efficacy analysis of secondary endpoint**

For the secondary endpoint the proportion of attacks treated with lasmiditan 100 mg and with lasmiditan 200 mg which respond as headache pain-free at 2 hours will be calculated for each 3 month period based on the treated migraine-level of the mITT population.

The proportion will be calculated as number of attacks which meet the criteria for headache pain-free at 2 hours divided by total number of treated attacks in each treatment group.

This analysis will be presented by treated migraine attack for total no. of attacks in each treatment group. This data will be presented for each three month period of time such as 0 – 3 months after randomization, > 3 – 6 months after randomization, > 6 – 9 months after randomization, > 9 – 12 months after randomization as well as for the entire study.

Headache pain-free is defined as a reduction in headache severity from mild (1), moderate (2), or severe (3) at baseline to none (0).

Treated migraines that do not have a headache pain severity rating at baseline will be excluded from the analysis. Treated migraines that do not have an associated headache pain severity rating at the two-hour time point will be assumed to have not achieved headache pain-free.

Subjects taking any rescue medication within the first two hours will be assumed to have not achieved headache pain-free. Subjects who use other medication prior to the study drug to treat the migraine attack will also be assumed to have not achieved headache pain-free.

Subjects who treat a no (0) severity migraine will not be included in this analysis.

Similar analysis will also be performed for Most Bothersome Symptoms Free at 2 hours post dose and Headache Pain Relief at 2 hours post dose under the same assumptions of sections 11.2.1.2 and 11.2.1.6 .

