#### **11.2.1.2 Most Bothersome Symptom Free (MBS-Free)**

MBS-free is defined as the absence of the associated symptom of migraine (either nausea, phonophobia, or photophobia) at 2-hour post-dose that was identified pre-dose as the most bothersome symptom. Subjects who record that no symptoms were present at baseline will be excluded from the key MBS analyses.

Subjects who do not provide a symptom rating at baseline will be excluded from the analysis except following possibility:

- Subjects who record at least one symptom present at baseline, but who do not designate one as most bothersome, will be treated as if all symptoms present are most bothersome and will be considered MBS-free at any time point post-dose only if all symptoms present at baseline are no longer present at that time point.

Subjects taking rescue medication within the first two hours, or who fail to record a symptom rating at 2 hours, will be assumed to have not achieved MBS-free.

The counts and percentages of which symptom was chosen as the most bothersome symptom will also be presented by treated migraine attack.

Subjects missing symptoms at baseline or at the summarized time point will not be summarized at that time point.

These analyses will be presented by treatment group, for the ITT and mITT populations, based on first dose and for ITT2nd dose rescue and recurrence population based on second dose. These presentations will be summarized on ITT and mITT migraine level analysis.

The endpoint of MBS-free will be summarized at the 0.5, 1, 2, 4, 24, and 48-hour post-dose time points. This summary will be repeated separately for each symptom (nausea, phonophobia, and photophobia) on the mITT and ITT population at treated migraine level.

This data will be summarized for the 1st, 2nd, 3rd, 4th, 5th, 10th, 15th, and 20th treated migraine.

For subjects that treated 5 or more migraines, MBS-free at 2 hours will be summarized across the first five treated migraines and as overall response for all treated migraines. Overall response for each subject in this subgroup is calculated by dividing the number of successful responses (responses at 2 hours) by total number of attacks treated.

Additionally, a time to MBS Free Kaplan-Meier analysis will be conducted on the first treated migraine for the subject-level ITT population by dose.

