#### **11.2.1.6 Headache Pain Relief**

Counts and percentages of the number of subjects with headache relief will be presented at the 0.5, 1, 2, 4, 24, and 48-hour post-dose time points. This summary will be presented by treatment group for the ITT population, ITT-2nd dose rescue and recurrence populations based on second dose at treated migraine level for each treated migraine attack.

Headache relief is defined as experiencing a moderate (2) or severe (3) headache at baseline which becomes mild (1) or none (0) at the summarized time point, or a mild (1) headache at baseline which becomes none (0) at the summarized time point for each treated migraine.

Treated migraines without a headache severity at baseline will be excluded. Treated migraines missing a severity assessment at a post-dose time point will not be categorized as pain relief.

This data will be summarized for the 1st, 2nd, 3rd, 4th, 5th, 10th, 15th, and 20th treated migraine.

For subjects that treated 5 or more migraines, headache pain relief at 2 hours will be summarized across the first five treated migraines and as overall response for all treated migraines.. Overall response for each subject in this subgroup is calculated by dividing the number of successful responses (responses at 2 hours) by total number of attacks treated.

Additionally, a time to headache pain relief Kaplan-Meier analysis will be conducted on the first treated migraine for the subject-level ITT population by dose.

Summary of headache pain relief will be presented for all treated migraine attacks for ITT population as overall numbers and by each quarter as defined in section 8.5.

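### SAP 11.1 fails attacks with early rescue or pre-dose medication for 2-hour pain-free, but 2-hour pain relief carries neither rule and MBS-free lacks the pre-dose rule

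*SAP*

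**What the plan says.** SAP 11.1 sets the handling rules for the secondary endpoint, 2-hour pain-free by 3-month period. On rescue: "Subjects taking any rescue medication within the first two hours will be assumed to have not achieved headache pain-free". On pre-treatment: "Subjects who use other medication prior to the study drug to treat the migraine attack will also be assumed to have not achieved headache pain-free". It closes by announcing similar summaries for MBS-free and for "Headache Pain Relief at 2 hours post dose under the same assumptions of sections 11.2.1.2 and 11.2.1.6".

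SAP 11.2.1.6 defines relief from severity scores at baseline and at the summarized time. It excludes attacks with no baseline severity, and its one failure rule is "Treated migraines missing a severity assessment at a post-dose time point will not be categorized as pain relief". It does not mention rescue or prior medication.

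SAP 11.2.1.2 has a rescue rule of its own, which scores such attacks as MBS-free failures; it begins "Subjects taking rescue medication within the first two hours, or who fail to record a symptom rating at 2 hours, will be assumed to have". It says nothing about medication taken before study drug.

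Protocol 10.6.1 treats as non-responders "Subjects taking rescue medication within the first two hours or who fail to record headache severity at 2 hours", and also those who used another drug before study drug, in the ITT and mITT analyses. That section defines only pain-free and MBS-free. Protocol 10.6.3.1 defines relief from severity and repeats neither rule.

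**The concern.** Three 2-hour endpoints are reported together, and the SAP scores the same attack differently across them. Because 11.1 names other sections as the source of assumptions for relief, a programmer who follows the text would build relief from severity scores only. An attack pre-treated or rescued early with a non-study drug would then be a relief success whenever the 2-hour score improved.

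Relief at 2 hours feeds the by-period and quarterly summaries, the attack-sequence tables, the summary for subjects with five or more attacks, and the three-attack consistency analysis in 11.2.1.4. The study has no control group to set the rates against. SAP 5.1 also drops the per-protocol population, which under Protocol 10.3.2 would have excluded subjects with rescue before 2 hours. No analysis in the SAP shows relief with these attacks counted as failures.

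**Working it through.** The plan states no rate or power figure for this endpoint, so there is nothing to reproduce. The check compares the rules first and then sizes the gap.

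**Rules side by side (2-hour endpoints)**

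| Endpoint | SAP section | Rescue before 2 h | Other drug before study drug |
|---|---|---|---|
| Pain-free | 11.1 | failure | failure |
| MBS-free | 11.2.1.2 | failure | no rule |
| Pain relief | 11.2.1.6 | no rule | no rule |

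**Three attacks traced through the text**

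1. Severe at dosing, a non-study analgesic at 1 hour, no pain at 2 hours. Pain-free: failure. MBS-free: failure. Relief: success.
2. Another drug first, then study drug; no pain and no MBS at 2 hours. Pain-free: failure. MBS-free: success. Relief: success.
3. A second dose of study drug at 1 hour. Under SAP 5.4 first-dose data stop at that dose. The stated exception, "if a second dose is taken before the 2-hour time point, the subject will still be included in the summary at 2 hours", counts the attack as a failure and names only pain-free and MBS-free. For relief the later 2-hour score is cut off, and the missing-score rule in 11.2.1.6 then makes it not relief.

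So an early second dose of study drug cannot yield first-dose relief, but early use of another analgesic can.

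**Reading the cross-reference more generously.** Suppose both named sections govern relief. The rescue rule in 11.2.1.2 is still worded for MBS-free alone, and neither section has a pre-dose rule.

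**Size.** Let f be the share of attacks with either kind of medication use, r the relief rate recorded in them, and c the relief rate in all other attacks.

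- As written: (1 − f) × c + f × r
- Under the pain-free convention: (1 − f) × c
- Difference: f × r, which is never negative

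All inputs below are assumptions. Differences are in percentage points.

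| f | r = 30% | r = 50% | r = 70% |
|---|---|---|---|
| 1% | 0.3 | 0.5 | 0.7 |
| 2% | 0.6 | 1.0 | 1.4 |
| 5% | 1.5 | 2.5 | 3.5 |
| 10% | 3.0 | 5.0 | 7.0 |

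Example with c = 60% and r = 50%:

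- f = 5%: 0.95 × 60 + 0.05 × 50 = 59.5% as written, against 57.0%.
- f = 10%: 0.90 × 60 + 0.10 × 50 = 59.0% as written, against 54.0%.

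If f differs between the arms, the difference in relief between 200 mg and 100 mg moves by (f1 − f2) × r between the two conventions. For 5% against 2% that is 0.9 to 2.1 points; for 10% against 5% it is 1.5 to 3.5 points (r from 30% to 70%).

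**The case against.** The best defence is that silence is not a decision. SAP 11.1 presents the relief summary as similar to one that contains both rules, and the SAP says it rests on the protocol, whose Headache Response section treats both kinds of attack as non-response. On that reading only wording is missing. This stands in part, since the text is ambiguous. But the sentence names its source of assumptions, and 11.2.1.2 and 11.2.1.3 (sustained pain-free) each write their own medication condition. A document that states such rules endpoint by endpoint cannot be relied on to carry them over unstated.

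Four stronger readings are tempting, and the documents do not support them.

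- **An undeclared departure from the protocol.** Protocol 10.6.1 defines only pain-free and MBS-free, and 10.6.3.1 leaves the rules out for relief. Whether the protocol covers relief is arguable.
- **Two conflicting values for 2-hour pain-free.** Section 11.2.1.1 restates neither rule, but it gives no definition of pain-free either, so it most naturally inherits 11.1.
- **A hidden drift over the year.** Nothing in the documents suggests that early use of other drugs grows. SAP 8.5 tabulates it by treatment group and quarter, so a rise would be visible beside the quarterly relief rates.
- **Relief rates that credit lasmiditan with other drugs' effect.** This is possible but not shown. The product f × r treats all relief in these attacks as due to the other drug and none as due to lasmiditan. Both behaviours also breach the dosing instructions in Protocol 8.5 and 9.1.7, which may keep f small.

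One limit remains. The SAP's ITT and mITT definitions are missing from the text available for this review, so an attack-level exclusion there cannot be ruled out. The protocol definitions contain none, and 11.1 would not need its pre-dose rule if mITT already removed those attacks.

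**Conclusion.** The inconsistency is in the text of the SAP. An attack with early rescue or pre-dose medication fails 2-hour pain-free but can count as relief, and a pre-treated attack can also count as MBS-free. The direction is certain: the relief rate as written is equal to or higher than under the pain-free convention. The size is unknown. The range of 0.3 to 7.0 points rests wholly on assumed shares of 1% to 10% and relief rates of 30% to 70%, and it measures the distance between two scoring conventions.

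The consequence is limited. Relief and MBS-free are additional endpoints, efficacy is descriptive, the secondary endpoint in 11.1 keeps both rules, and the study's primary purpose is safety. It should still be settled before the tables are programmed, because the reported rates depend on it and the correction is cheap.

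**What to change.** State in SAP 11.2.1.6 and 11.2.1.2 that the two medication rules of 11.1 apply to every 2-hour endpoint: pain-free, MBS-free and pain relief. Repeat this in 11.2.1.1 and 11.2.1.4 for clarity. Word the rules per attack and limit them to the 2-hour summaries. Failing pre-treated attacks out to 48 hours while early-rescued attacks fail only at 2 hours would create a new inconsistency.

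Use the derivation that 11.1 already needs. The categories listed in SAP 8.5 (none, before, or after the 2-hour assessment) are not enough, because they do not separate use before study drug from use after it.

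If the different handling of relief is intended, say so with a reason in SAP 5.1 and show 2-hour relief both ways.

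The cost is a few sentences and the reuse of one derivation, with no new data. Reported relief and MBS-free rates may fall slightly.

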## **11.2 Efficacy analysis of additional endpoints**

### **11.2.1.1 Headache Pain-Free**

The endpoint of headache pain-free will be summarized in proportion at the 0.5, 1, 2, 4, 24, and 48-hour post-dose time points. This summary will be presented by treatment group for the ITT and mITT populations, based on first dose and for ITT2nd dose rescue and recurrence population based on second dose. These presentations will be summarized on ITT and mITT treated migraine level analysis.

Treated migraines with a mild, moderate, or severe headache severity at the time of dosing will be

the reference subjects for this summary. Treated migraines without a headache severity at baseline, or with a headache severity of 'none' will be excluded. Treated migraines missing a severity assessment at a post-dose time point will not be categorized as pain-free.

This data will be summarized for the 1st, 2nd, 3rd, 4th, 5th, 10th, 15th, and 20th treated migraine.

Similarly, data will be presented for subjects with only moderate or severe pain at dosing for mITT Population at treated migraine level.

For subjects that treated 5 or more migraines, headache pain-free at 2 hours will be summarized across the first five treated migraines and as overall response for all treated migraines. Overall response for each subject in this subgroup is calculated by dividing the number of successful responses (responses at 2 hours) by total number of attacks treated.

Additionally, a time to headache pain-free Kaplan-Meier analysis will be conducted on the first treated migraine for the subject-level ITT population by dose.

Summary of headache pain free will be presented for all treated migraine attacks for mITT population as overall numbers and by each quarter as defined in section 8.5.

#### **11.2.1.2 Most Bothersome Symptom Free (MBS-Free)**

MBS-free is defined as the absence of the associated symptom of migraine (either nausea, phonophobia, or photophobia) at 2-hour post-dose that was identified pre-dose as the most bothersome symptom. Subjects who record that no symptoms were present at baseline will be excluded from the key MBS analyses.

Subjects who do not provide a symptom rating at baseline will be excluded from the analysis except following possibility:

- Subjects who record at least one symptom present at baseline, but who do not designate one as most bothersome, will be treated as if all symptoms present are most bothersome and will be considered MBS-free at any time point post-dose only if all symptoms present at baseline are no longer present at that time point.

Subjects taking rescue medication within the first two hours, or who fail to record a symptom rating at 2 hours, will be assumed to have not achieved MBS-free.

The counts and percentages of which symptom was chosen as the most bothersome symptom will also be presented by treated migraine attack.

Subjects missing symptoms at baseline or at the summarized time point will not be summarized at that time point.

These analyses will be presented by treatment group, for the ITT and mITT populations, based on first dose and for ITT2nd dose rescue and recurrence population based on second dose. These presentations will be summarized on ITT and mITT migraine level analysis.

The endpoint of MBS-free will be summarized at the 0.5, 1, 2, 4, 24, and 48-hour post-dose time points. This summary will be repeated separately for each symptom (nausea, phonophobia, and photophobia) on the mITT and ITT population at treated migraine level.

This data will be summarized for the 1st, 2nd, 3rd, 4th, 5th, 10th, 15th, and 20th treated migraine.

For subjects that treated 5 or more migraines, MBS-free at 2 hours will be summarized across the first five treated migraines and as overall response for all treated migraines. Overall response for each subject in this subgroup is calculated by dividing the number of successful responses (responses at 2 hours) by total number of attacks treated.

Additionally, a time to MBS Free Kaplan-Meier analysis will be conducted on the first treated migraine for the subject-level ITT population by dose.

Summary of MBS free will be presented for all treated migraine attacks for mITT population as overall numbers and by each quarter as defined in section 8.5.

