### **5.5 Handling of Missing Values**

Subjects who fail to record information at a particular analysis time point will have that value considered missing in the respective table, unless otherwise specified.

The endpoints of headache severity and MBS presence at 2 hours post-dosing are two exceptions to this: (1) Subjects who fail to record a headache severity at 2 hours for each treated migraine

will be assumed to have not achieved headache pain-free status, and (2) subjects who fail to record the absence of a symptom at 2 hours at each treated migraine that was considered their MBS at baseline will be assumed to have not achieved MBS-free status. This will be considered for data presented for each treated migraine attack.

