### **11.2.1.4 Consistency Analyses**

This analysis will be performed on ITT subject level population.

For subjects that treated 3 or more migraines, headache pain-free at 2 hours, headache relief at 2 hours and MBS free at 2 hours will be summarized across the first three treated migraines with headache severity assessments. The number and percentage of subjects reaching pain-freedom and pain relief will be reported for the following categories: 0 of 3 migraines meeting the criteria, 1 of 3 migraines meeting the criteria, 2 of 3 migraines meeting the criteria, 3 of 3 migraines meeting the criteria, and 2 or 3 of 3 migraines meeting the criteria.

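### SAP 11.2.1.2 gives two opposing rules for a missing 2-hour MBS rating, and its exclusion rule is likely to overstate MBS-free rates at 4, 24 and 48 hours

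*SAP*

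**What the plan says.** SAP 11.2.1.2 gives two instructions for a missing post-dose rating. Subjects "who fail to record a symptom rating at 2 hours, will be assumed to have not achieved MBS-free". Further down: "Subjects missing symptoms at baseline or at the summarized time point will not be summarized at that time point". The section also states: "The endpoint of MBS-free will be summarized at the 0.5, 1, 2, 4, 24, and 48-hour post-dose time points". Two hours is on that list, and the exclusion sentence makes no exception for it. SAP 11.1 applies the assumptions of 11.2.1.2 to the 2-hour MBS-free analysis by three-month period.

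Four other places bear on the point:

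- **SAP 5.5** sets the default. A subject with no entry at a time point "will have that value considered missing in the respective table, unless otherwise specified". It then names two exceptions, headache severity and MBS at 2 hours, and counts missing values of both as failures.
- **Protocol 10.6.2** also treats missing 2-hour pain-free and MBS-free data as non-response, with a sensitivity analysis that excludes missing data. SAP 5.1 drops that sensitivity analysis.
- **SAP 11.2.1.1** says of pain-free: "Treated migraines missing a severity assessment at a post-dose time point will not be categorized as pain-free". SAP 11.2.1.6 has the matching rule for pain relief. Both apply at every post-dose time point.
- **SAP 5.4** says: "Any analyses based on first dose will only include data observed up to the time of dosing with a second dose". Its one exception concerns the 2-hour endpoints: an attack re-dosed before 2 hours stays in the summary and counts as neither pain-free nor MBS-free.

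**The concern.** A programmer working from 11.2.1.2, or from 11.1, which points to it, can build either denominator for the 2-hour MBS-free rate and cite a sentence in support. Nothing in the output would show which was used.

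At the other time points the text is clear, but it differs from the neighbouring endpoints. A missing rating leaves the MBS-free denominator, while a missing severity rating stays in the pain-free and pain-relief denominators as a non-response. The tables share arms and time points, so readers will compare them without knowing that the denominators differ.

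The missing data after 2 hours are also not likely to be a random subset. Under 5.4 a second dose ends the first-dose data, and SAP section 5 says the e-diary then cancels the remaining first-dose alarms. SAP section 4 defines second doses as following either no pain freedom at 2 hours (rescue) or the return of pain (recurrence). The attacks that leave the later MBS-free denominator are therefore selected for a poor pain course after the first dose.

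**Working it through.** The plan states no MBS-free rate, missing-data rate or sample-size calculation for this endpoint, so there is no figure of its own to reproduce. The check is a comparison of rules, followed by arithmetic on assumed inputs.

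**Step 1. Rules side by side for a missing post-dose rating**

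| Endpoint | At 2 hours | At 0.5, 1, 4, 24, 48 hours |
|---|---|---|
| MBS-free (11.2.1.2) | failure in one sentence, excluded in another | excluded |
| MBS (5.5) | failure | left as missing |
| Pain-free (11.2.1.1) | failure | failure |
| Pain relief (11.2.1.6) | failure | failure |

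The direct contradiction is confined to 2 hours. Because SAP 5.1 removed the analysis that excludes missing data, the exclusion sentence cannot be read as a planned second analysis.

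**Step 2. Size of the denominator effect**

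Let p be the MBS-free rate among rated attacks and m the share with no rating. Exclusion reports p and the failure rule reports p(1 − m). The gap is p × m and the ratio is 1/(1 − m). Both inputs are assumptions.

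- p = 40%, m = 10%: 0.40 × 0.90 = 36%, a gap of 4 points.
- p = 40%, m = 20%: 0.40 × 0.80 = 32%, a gap of 8 points.
- Over p = 30% to 60% and m = 2% to 30%, the gap runs from 0.30 × 0.02 = 0.6 points to 0.60 × 0.30 = 18 points.

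**Step 3. Effect of mixing rules over time**

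Suppose 40% of rated attacks are MBS-free at both 2 and 4 hours, with the same share missing. With failure at 2 hours and exclusion at 4 hours, the table shows 36% then 40% at m = 10%, and 32% then 40% at m = 20%. That rise comes from the change of rule alone.

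**Step 4. Is exclusion biased upward?**

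Let q be the true MBS-free rate among unrated attacks. The true rate is p(1 − m) + qm, so exclusion is off by m(p − q) and the failure rule by −qm. At p = 40% and m = 20%:

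| q | Exclusion | Failure rule |
|---|---|---|
| 0% | +8 points | 0 |
| 20% | +4 points | −4 points |
| 40% | 0 | −8 points |
| 60% | −4 points | −12 points |

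Exclusion overstates the rate only if unrated attacks do worse than rated ones.

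**Step 5. The second-dose cut**

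Let d be the share of attacks re-dosed before the time point and r the MBS-free rate among the rest. Exclusion shows r; counting re-dosed attacks as failures gives r(1 − d). With r = 50%, d = 10%, 20% and 30% give 45%, 40% and 35%. With r = 70%, they give 63%, 56% and 49%. These shares are also assumed.

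**The case against.** The strongest reply on the 2-hour conflict is that the SAP already settles it. Section 5.5 names 2-hour MBS as an exception and counts it as a failure, 5.4 treats re-dosing before 2 hours the same way, and Protocol 10.6.2 agrees. This stands. A reader might infer that the plan supports two legitimate 2-hour values. It does not: one rule prevails and the exclusion sentence is a drafting error. It still needs correcting, because 11.2.1.2 is the detailed specification.

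A second reply is that exclusion at the other time points is simply the 5.5 default. That is true, but pain-free and pain relief were given an explicit departure from the default and MBS-free was not, with no reason stated.

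Third, re-dosing is defined by headache pain, not by MBS, so a re-dosed attack may be MBS-free. This also stands. It makes the upward direction likely rather than proven, and leaves the size open.

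Several stronger readings are tempting but unsupported:

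- **Re-dosed attacks count as failures in the later pain-free table.** SAP 5.4 keeps re-dosed attacks in only for the 2-hour endpoints, and 11.2.1.1 does not say that data cut at a second dose count as missing. Their handling after 2 hours is unclear for pain-free as well.
- **Sustained benefit is overstated.** No sustained MBS endpoint exists. The sustained endpoint in 11.2.1.3 is pain-free, and it already requires 2-hour pain freedom and no later medication.
- **The consistency analysis skips failures.** Section 11.2.1.4 summarizes "across the first three treated migraines with headache severity assessments" without saying which assessment is required. An attack with a baseline rating and no 2-hour rating could qualify and count as a failure under 5.5. This is wording to clarify, not a demonstrated departure.

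**Conclusion.** At 2 hours there is a real contradiction inside 11.2.1.2, carried into 11.1, and the rest of the plan resolves it in favour of counting a missing rating as a failure. At the other post-dose time points MBS-free uses a different denominator rule from pain-free and pain relief. At 4, 24 and 48 hours exclusion is likely to overstate MBS-free rates, because second doses remove attacks with pain failure or recurrence. That direction assumes that attacks with poor pain outcomes also tend to have worse MBS outcomes, which is plausible but not shown in the documents.

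The size is unknown. The illustration of 40% falling to 36% to 32% rests on an assumed rate among rated attacks and an assumed 10% to 20% missing. The stakes are limited: efficacy is descriptive, the primary endpoint is safety, and no test or sample size depends on MBS-free. The point is worth correcting because the reported rates would otherwise rest on an ambiguous rule.

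**What to change.** 1. In SAP 11.2.1.2, delete the words that extend the exclusion to the time point being summarized, so that the sentence covers missing baseline symptoms only.
2. State that a missing post-dose MBS rating counts as not MBS-free at every time point, including a first-dose rating cut off by a second dose. Amend 5.5 to match.
3. State the same handling of re-dosed attacks for pain-free and pain relief, since 5.4 leaves it open after 2 hours.
4. Keep both baseline exclusions: attacks with no symptom at baseline and attacks with no baseline symptom rating, together with the existing provision for attacks where symptoms are present but none is named as most bothersome.
5. Report the number of attacks missing and the number re-dosed, by arm and time point. Arm matters because the current protocol (8.1) permits a second dose only for subjects randomized to 100 mg, while the SAP study summary (2.1) describes it for both arms; those passages should be reconciled.
6. In 11.2.1.4, say which severity assessment makes an attack eligible, and count missing 2-hour data as failure in line with 5.5.

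The cost is SAP wording and programming. MBS-free rates will be slightly less favourable, and they will be conservative if some unrated or re-dosed attacks were in fact MBS-free. SAP 5.6 plans the same tables for the final lock as for the May 2018 lock, so any change of rule between the two should be footnoted.
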